12.3.3 Expected SAEs and adverse events

Certain adverse events are common to CF and associated medications. Expected SAEs must be reported in the annual safety report. Hospitalisation as a result of an exacerbation will be recorded in the study database and not be reported as an SAE.

Expected AEs in relation to medications or common in patients with CF

- 1. Acute FEV₁ drop >15% after 1st dose of medication
- 2. Increased productive cough
- 3. Nasal congestion or stuffy nose
- 4. Chest congestion
- 5. Wheezing
- 6. Chest pain or chest discomfort
- 7. Voice alteration/change
- 8. Dysponea (breathlessness)
- 9. Haemoptysis (coughing blood)
- 10. Rhinitis
- 11. Headache
- 12. Crackles in lung
- 13. Throat irritation/ sore throat
- 14. URTI
- 15. Sinusitis
- 16. Deafness

- 17. Indigestion / reflux
- 18. Tonsillitis
- 19. Joint pain
- 20. Decreased appetite
- 21. Fatigue
- 22. Headache
- 23. Distal intestinal obstructive syndrome
- 24. Fever
- 25. Otitis media or ear infection
- 26. Conjunctivitis
- 27. Pneumothorax
- 28. Decreased exercise tolerance
- 29. Pyrexia
- 30. Abdominal pain
- 31. Influenza
- 32. Pseudomonas infection
- 33. Vomiting
- 34. Diabetes
- 35. Pneumonia

12.3.4 Reporting

Adverse events and SAEs can be reported for participants at any stage of their trial participation. A member of the site study team (interventionist, clinician or other) will enquire about any adverse events at routine clinic appointments. These will be record on the adverse event section of the paper CRF and database. The event will be assessed by the local Principal Investigator and the form will be kept in the site file. Serious adverse events will be reported in the periodic safety reports to the research ethics committee and Trial Steering committee.

All adverse events (serious or other based on the definitions above) will be recorded on the case report form and details will be **entered on the study database within 1 week of completing the paper form**. Any SAEs which are deemed related to the trial intervention, the site will complete the paper CRF and **fax this form to the CTRU within 24 hours of becoming aware of the event** in order for the CTRU to report this event to the Sponsor and the main REC within the required timeframes (15 days).

•

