every standard clinic visit. Where participants have not attended the hospital for a period of over 3 months, the Interventionist will administer the Clinic visit behavioural questionnaire and the EQ5D-5L over the phone every 3 months.

Table 4. CFHealthHub data (CFHealthHub group only)

	Completed by?	Baseline (intervention) visit	At intervention visit s with interventionist	Between sessions	At clinic visits	At 12 months
Clinician metrics						
Adherence data*	PWCF	•	•	•	•	•
Recommendation of modules by interventionist	Interventionist	•	•	-	•	-
Feed back to participant their adherence data screens (data click)	Interventionist	•	•	-	•	-
Check prescription with participant	Interventionist	•	•	-	•	-
Order of clicks	CFHH	•	•	-	•	-
Interventionist responds to patient changing prescription	Interventionist	-	•	•	•	•
Monthly check on prescription +	Interventionist / CTRU	•	•	•	•	•
Time in and out preparation	Interventionist /CFHH	•	•	-	-	•
Time in and out with patient	Interventionist /CFHH	•	•	-	-	•
Time in and out review	Interventionist /CFHH	•	•	-	-	•
Patient metrics						
Adherence (number of nebulized doses taken per day.) ¹	PWCF	•	•	•	•	•
Duration of inhalation	Nebuliser	•	•	-	-	-
Accessing CFHealthHub – look at adherence data	PWCF	•	•	-	-	-
Accessing CFHealthHub – look at 'My Toolkit'	PWCF	•	•	-	-	-
Accessing CFHealthHub problem solving / education / talking heads pages outside of 'My Toolkit'	PWCF	•	•	-	-	=
Accessing CF HealthHub – first to last click in a session	PWCF	•	•		-	-
	PWCF					X

^{*}Adherence data collected for both research and control arms

Data at the 12 month follow up visit may be collected by the interventionist within+/-4 weeks of the due date.

⁺ Monthly prescription checked by CTRU centrally to alert local interventionists to any potential changes

¹To be broken down in statistical analysis plan.

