Figure 6. Participant timeline for the external pilot RCT Identification and approach, by letter, following up with phone call (pre-Consent form): 1) PWCF identified through the CF registry 2) Screened for eligibility (pre-screening tool): Inclusion: PWCF who have data within the CF registry aged > 16 years and taking inhaled mucolytics or antibiotics via a chipped nebuliser (e.g eTrack or I-Neb) or able and willing to take via eTrack or I-Neb. Exclusion: PWCF who are post-lung transplant or on the active lung transplant list, patients receiving palliative care, with palliative intent, for whom trial participation could be a burden, patients lacking in capacity to give informed consent or using dry Enrollment powder devices to take antibiotics or mucolytics. 3) Direct care team 1) Sends potential participant PIS and introductory letter by post and Interventionist follow's up by phone within 1 week to ensure they have received the information and allow an opportunity for questions AND/OR 2) Direct care team gives patients written information during routine clinic visit and asks permission to follow up the patient with a phone call to answer further questions and discuss involvement. CONSENT VISIT, at home or in clinic: 1) Screening form completed (confirmation of eligibility) 2) Informed consent 3) Data Collection: Intravenous days in last registry year; BMI; FEV1; EQ-5D-5L; PAM-13; CHAOS; MAD-3; SRBAI; CFQ-R; PHQ-8; GAD-7; COM-BMQ; Exacerbations form; subjective adherence question Participant given data logging nebuliser and Qualcomm hub. Randomisation (n~556): ACtiF interventionists randomises using web-based system between consent and baseline visits and informs participant ideally within 1 week of consent visit. Intervention arm Allocation Research: Monitoring and feedback (N=278): Initial Intervention visit: at home or in clinic (2-6 weeks from consent visit) (1 hour) 1) Adherence data uploaded, fed back and reasons for suboptimal adherence discussed in order to identify problems to solve using the Adherence Support Process; Control arm 2) Intervention chosen based on barrier from "library" in the Usual care n=278: Adherence Support Process; Adherence data uploaded. Care team and PWCF remain 3) Supportive contact offered via phone or email; and, blind to adherence data 4) Participants given personal access to CFHealthHub Manualised intervention delivered by trained researcher in initial intervention visit and subsequent visits normally every 4-6 weeks from this initial visit till six months visit (see below) ACtiF Researcher collects exacerbation data Data collected: Exacerbations form triggered by commencement of IV antibiotics; EQ5D-5L at both start and end of exacerbation episode Routine Clinic Visits: Data collected from all routine clinic visits after the date of consent. Follow-up Data collected by ACtiF researcher except where specified: (i) FEV1; (ii) subjective adherence question (iii) exacerbations form (iv) EQ5D-5L (v) Behavioural questionnaire. Adherence data continued to be uploaded to CFHealthHub Monthly follow up by CTRU researcher and/or ACtiF interventionist Monthly check of adherence data and contact with participant where missing adherence data or requirement to follow up on changes to prescription 12 month visit Primary clinical outcome: Number of exacerbations (Fuchs criteria) Secondary outcomes: BMI; FEV1; EQ-5D-5L; PAM-13; CHAOS; MAD-3; SRBAI; CFQ-r; PHQ-8; GAD-7; COM-BMQ; Exacerbations form; Other SAE's, resource use questionnaire

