12.3 Harms (safety assessments)

12.3.1 Serious Adverse Events

Trial sites are to report SAEs in conjunction with the CTRU standard operating procedure PM004 (Adverse events and serious adverse events). The definition of an SAE is as follows:

- results in death;
- is life-threatening* (subject at immediate risk of death);
- requires in-patient hospitalisation or prolongation of existing hospitalisation;**
- results in persistent or significant disability or incapacity;

- consists of a congenital anomaly or birth defect; or,
- is another important medical event that may jeopardise the subject.***
- * 'life-threatening' refers to an event in which the patient was at risk of death at the time of the event; it does not refer to an event which hypothetically might have caused death if it were more severe.
- **Hospitalisation is defined as an inpatient admission, regardless of length of stay, even if the hospitalisation is a precautionary measure for continued observation. Hospitalisations for a pre-existing condition, including elective procedures that have not worsened, do not constitute an SAE.
- ***Other important medical events that may not result in death, be life-threatening, or require hospitalisation may be considered a serious adverse event/experience when, based upon appropriate medical judgment, they may jeopardise the subject and may require medical or surgical intervention to prevent one of the outcomes listed in this definition.

It is not anticipated that there will be many SAEs related to the behaviour change intervention. We will report any SAEs which are deemed related to the trial intervention and unexpected to the Sponsor within the specified timeframes below (12.3.4).

12.3.2 Adverse events we require reporting:

We do require that sites report any new diagnosis of depression and/or anxiety which requires treatment with medication or psychological therapy e.g. Cognitive Behavioural Therapy (CBT).

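### Section 12.3.4 puts adverse event enquiry at routine clinic appointments, but Table 3 and Figure 6 schedule SAE collection only at 12 months; the passages need reconciling

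*Protocol*

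**What the plan says.** **Safety section.** Section 12.3.4 gives three instructions that bear on timing.
- On enquiry: "A member of the site study team (interventionist, clinician or other) will enquire about any adverse events at routine clinic appointments".
- On when reports may be made: "Adverse events and SAEs can be reported for participants at any stage of their trial participation".
- On SAEs judged related to the intervention, the site must complete the paper form and "fax this form to the CTRU within 24 hours of becoming aware of the event".

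Section 12.3.2 adds one named non-serious event: "We do require that sites report any new diagnosis of depression and/or anxiety which requires treatment", whether by medication or by psychological therapy.

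**Schedule.** In Table 3 (section 7.4) the row Other SAEs has its only bullet at 12 months from consent, with dashes under clinic visits and exacerbation episodes. There is no row for non-serious adverse events or for depression or anxiety diagnoses. The EQ-5D-5L footnote to Table 3 covers people who have not attended for more than 3 months: "the Interventionist will administer the Clinic visit behavioural questionnaire and the EQ5D-5L over the phone every 3 months".

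For routine clinic visits Figure 6 reads: "Data collected by ACtiF researcher except where specified: (i) FEV1; (ii) subjective adherence question (iii) exacerbations form (iv) EQ5D-5L (v) Behavioural questionnaire". For the 12-month visit its list ends: "Exacerbations form; Other SAE's, resource use questionnaire".

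**Analysis.** Section 11.1 plans to summarise SAEs and all adverse events by arm, as numbers and percentages.

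**The concern.** The protocol describes harms collection in two places that do not match. The safety section expects staff to ask at routine clinic appointments. The table and figure that set out what to collect at each contact show nothing to ask there.

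A site that builds its visit worksheets from Table 3 or Figure 6 could leave the question out. Events would then come to light through the 12-month visit, through spontaneous reports, or through whatever contact happens to occur. The first may be late and the other two are uneven. The trial has no data monitoring committee (section 12.1), and the steering committee relies on periodic safety reports, so timely capture matters.

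A second issue is comparability. Participants in the CFHealthHub arm have review visits with the interventionist that controls do not have, and only the statisticians are blinded (section 9.4). If detection depends on incidental contact, it may differ by arm, and section 11.1 compares the arms on exactly these events.

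**Working it through.** No formula applies, because the plan states no event rate or detection rate. The check sets the passages side by side, contact by contact.

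| Contact | Arms | Section 12.3 | Table 3 | Figure 6 |
|---|---|---|---|---|
| Routine clinic visit | both | adverse event enquiry | dash for Other SAEs; no row for other events | five items, none an AE or SAE |
| Exacerbation episode | both | no enquiry specified | dash for Other SAEs | exacerbations form and EQ-5D-5L |
| 3-monthly phone contact for non-attenders | no arm restriction stated | no enquiry specified | behavioural questionnaire and EQ-5D-5L (footnote) | not shown |
| 12-month visit | both | no enquiry specified | bullet for Other SAEs | Other SAEs listed |
| Intervention review visits | intervention only | no enquiry specified | no column | no AE or SAE item |

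1. **Number of scheduled points.** Table 3 and Figure 6 each give one scheduled SAE collection point, at 12 months. Section 12.3.4 gives routine clinic appointments, plus reporting at any stage.

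2. **Is it an artefact of the broken table?** Probably not. The Table 3 row has two blank cells (consent and baseline) after extraction, but the dashes and the bullet are legible, and Figure 6 shows the same pattern in prose. Figure 6 is captioned for the external pilot and keeps some pilot wording. Its content has been updated to this trial, however: about 556 randomised, 278 per arm, and a 12-month visit.

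3. **Do the other provisions close the gap?** Permission to report at any stage does not tell anyone to ask. The 24-hour rule starts only when the site becomes aware of an event, and it covers only SAEs judged related to the intervention. Section 12.3.1 refers to a CTRU operating procedure, which is not shown and which cannot settle a conflict inside the protocol.

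4. **Depression and anxiety.** PHQ-8 and GAD-7 are taken at consent and at 12 months in both arms. They grade symptoms and do not record a new diagnosis or its treatment, so they do not replace the report that section 12.3.2 requires.

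5. **What is outside the gap.** Section 12.3.3 keeps admissions for exacerbation out of SAE reporting because they are recorded separately. The gap therefore concerns other SAEs and the depression and anxiety diagnoses.

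6. **Difference between arms.** The clinic enquiry and the 12-month visit both apply to both arms, so the contradiction alone creates no imbalance. The asymmetry lies in the extra contact: section 6.4.4.4 provides review visits for the CFHealthHub group until the end of the study, and section 6.4.4 has interventionists pass on concerns that arise while working with participants.

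**The case against.** The best defence is that adverse event reporting here is event-driven and governed by section 12.3, not by Table 3. Section 12.3.4 still binds sites, nothing in the schedule cancels it, and adverse events have their own section in the paper form and database. A missing row in a schedule does not prove a missing form. The protocol also classes the trial as low risk. All of this stands, and it limits the point to an inconsistency with a practical consequence. It does not remove the inconsistency, because the schedule tells staff what to do at each contact and omits the enquiry.

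The defence also rightly blocks some stronger inferences.
- A reader might infer that SAEs rest on a single question with up to a year's recall. The resource use form (section 7.1.2) takes unscheduled inpatient stays from hospital notes and the NHS electronic system, so many admissions leave a record that does not depend on memory.
- A reader might take the 20% loss allowance in section 8.1.2 (556 − 444 = 112 participants) as the number with no safety contact. It is a sample size allowance. Those people may have attended clinics before being lost, and the figure would matter only if the clinic enquiry never took place.
- A reader might infer that non-attenders are never asked. The footnote lists what the phone contact includes and does not say that nothing else may be asked. Anyone who returns to clinic comes back under section 12.3.4.

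**Conclusion.** The inconsistency holds. Table 3 and Figure 6 omit the clinic-visit enquiry that section 12.3.4 requires. The event named in section 12.3.2 has no place in Table 3, and the phone contact for non-attenders lists no adverse event question. The consequence is a risk of less complete harms data at sites that follow the schedule, with detection left partly to incidental contact.

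A reader might go further and conclude that the by-arm percentages in section 11.1 are biased, with more events found in the intervention arm. The document does not show that. It schedules no adverse event enquiry at intervention visits, and both documented enquiry points cover both arms. Extra contact with unblinded staff makes unequal detection plausible. Its size cannot be derived from the document.

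The conclusion rests on two assumptions: that at least some sites work from Table 3 or Figure 6, and that the adverse event form does not itself prompt an enquiry at each clinic visit. The point is modest, but the remedy goes beyond tidying because it improves safety capture and makes ascertainment more even between arms.

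**What to change.** Reconcile Table 3 and Figure 6 with section 12.3.4:

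- Add one item, *SAE / new depression or anxiety*, at routine clinic visits in both, and keep the 12-month item.
- Add the same item to the existing 3-monthly phone contact for non-attenders.
- Use identical wording and timing in both arms.
- Record on the form where each report came from (clinic enquiry, phone contact, 12-month visit, intervention visit, spontaneous report), so that any difference in detection can be seen.
- Keep every event in the analysis, whatever its source. Leaving out those found at intervention visits would remove harms from one arm only, to correct a bias that has not been demonstrated.

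The cost is a small amendment to the table, figure and case report form, and about a minute at contacts that already take place. No new visits or staff are needed.

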12.4 Auditing

The sponsor will permit monitoring and audits by the relevant authorities, including the Research Ethics Committee. The investigator will also allow monitoring and audits by these bodies and the sponsor, and they will provide direct access to source data and documents.

12.5 Finance and indemnity

The trial has been financed by the NIHR and details have been drawn up in a separate agreement. This is an NHS sponsored study. If there is negligent harm during the clinical trial when the NHS body owes a duty of care to the person harmed, NHS Indemnity will cover NHS staff, medical academic staff with honorary contracts and those conducting the trial. NHS Indemnity does not offer no-fault compensation and is unable to agree in advance to pay compensation for non-negligent harm. Ex-gratia payments may be considered in the case of a claim.

13. Ethics and dissemination

13.1 Approvals

The trial will be conducted subject to Research Ethics Committee favourable opinion including any provisions for site specific assessment. The application will be submitted through the IRAS central allocation system. The approval letter from the ethics committee and copy of approved patient information leaflets, consent forms and any ethically approved questionnaires will be present in the site files before initiation of the study and patient recruitment. Local research governance approvals will be sought from all participating research sites. This clinical trial will be conducted in accordance with Good Clinical Practice Guidelines and CTRU standard operating procedures. MHRA approval is not required for this study.

13.2 Protocol amendments

The investigator will be updated following an amendment to the protocol or study documents. The new documents, REC approval, R&D approval, HRA assessment letter and any other appropriate documentation surrounding the amendment will be sent to the site via a "site file update". The sites will receive the documents with a site file update sheet, detailing where to file the amended documents and which documents to supersede. If there are any significant changes to the study procedures or eligibility criteria sites will be notified by a combination of email, telephone, newsletters or additional project training when required.

In relation to informing REC, if any study documents require amending, the changes will be discussed with the sponsor and either a substantial (via IRAS and HRA) or minor amendment (notification via email) will be submitted to REC and HRA. Following REC acknowledgment and approval (when applicable) other appropriate approvals will be obtained i.e. HRA and R&D approval.

If a protocol amendment requires participants to be re-consented they will be informed of the amendment by an updated participant information sheet and will be asked to re-consent to the study. Trial registries, journals and regulators will be updated regarding protocol amendments when appropriate.

13.3 Consent

Consent for the main trial:

The ACtiF trial interventionist or local PI at the site will be responsible for taking informed consent from potentially eligible trial participants face to face at home or in clinic. Any researcher or clinical member of the team taking informed consent will be trained in study procedures and GCP. Participants will have the option to specify whether they are interested in being approached for the qualitative interviews and audio recordings. However, they do not have to consent to these to be involved in the main study.

Consent for the interviews:

Consent for interviews (participant, interventionist or MDT member) will separately be taken by the qualitative researcher. Participants can participate in the main trial but choose to not take part in the qualitative research.

13.4 Confidentiality

Participant confidentiality will be respected at all times. Participant names and contact details will be collected and entered on the prospect database. Access to these personal details will be restricted to users with appropriate privileges only. All users who do not require access to identifiable data will only identify data by participant ID number, and no patient identifiable data will be transferred from the database to the statistician.

Trial documents (paper and electronic) will be retained in a secure location during and after the trial has finished. All source documents will be retained for a period of 5 years following the end of the trial. Where trial related information is documented in the medical records – those records will be retained for 5 years after the last patient last visit. Each site is responsible for ensuring records are archived and the information supplied to the Chief Investigator.

Any participant data held within CFHealthHub will be stored on a secure server at the University of Manchester. CFHealthHub complies with the Data Protection Act and follows best practice guidelines on security and information governance. Encrypted channels are used to transfer any data to and from the web and mobile application platforms. All user interaction with the CFHealthHub server and each action performed by a user will be logged. An audit log contains the username of the user performing the action, the date & time of the action, short description of the action performed. All users are authenticated via a secure password with access to the system restricted on a role basis.

